Per Table 4, an observed prevalence of 25% among a sample of 1,000 individuals will yield a half-width of a 95% confidence interval less than 4.64% (i.e., a confidence interval [20.36%-29.64%]).

Similarly, an observed prevalence of 5% among a sample of 1,000 individuals will yield a half-width of a 95% confidence interval less than 1.71% (i.e., a confidence interval [3.29%-6.71%]).

To reach a sample of 1,000 HIV-infected men and women ages 18-49 years, sampling will also take into consideration expected non-response rates and proportions of pre-cohort survey participants who will be ineligible due to inclusion/exclusion criteria.

7.3 Clustering and Sample Weighting in Analysis

As described in Section 7.2 the sample size calculations account for loss to follow-up, refusal, household size, the estimated proportion of the population in the age range, and non-contact (inability to contact). In addition, a design effect of 1.25 is used to ensure adequate power to detect differences in the presence of clustering in the outcome expected because of the two stage sampling design. As households are sampled at random from each enumeration area, we expect only a modest effect of clustering within enumeration areas. However clustering of new infections within a household may occur at a higher frequency than expected. A sensitivity analysis is planned to address the potential effect of clustering of incident infections within households on the primary population incidence comparison. Note that the analyses are independently conducted by gender, thus clustering of infection only impacts the estimates if two men or two women in the same household become HIV infected during the study. Bootstrap resampling methods will be implemented that randomly select one individual from each household to investigate the influence of clustering on the population estimates.

The use of samples weights is planned in analysis, as typically required to achieve population estimates from a two stage sampling design. All estimation of national rates will use appropriate sampling weights to achieve estimates representative of the Swaziland population aged 18-49. Three different types of weighting will be combined to define the sample weights: first-stage ratio adjustment; non-response adjustment; and post-stratification weighting. The two-stage sampling design provides for an equal probability weighting for selection of the enumeration areas in four regions and random

selection of households in each enumeration area. The sample selected will define first stage ratio adjustment weights that account for the probability of each respondent case being selected. Demographics information gathered about non-respondent households and non-respondent individuals will be used to compute sample weights that adjust for household and unit non-response. Post stratification weights may also be used to match the distribution of age and gender of the 2007 (or most recent) DHS.

Estimates from the baseline data of the cohort will use sample weights computed for the baseline cohort. Estimates from the 6 month follow-up will use sample weights computed for the cohort retained at 6 months, where the non-response weights will use information from both the non-response at baseline and the loss-to-follow-up non-response.

While sample weighting can be used to attempt to correct for potential bias arising from non-response and attrition, if the study achieves high response rates and high retention rates the need for non-response sample reweighting can be minimized .

8.0 DATA HANDLING AND ANALYSIS

8.1 Data Analysis Plan

8.1.1 Consideration of M&E/Program Performance Data

The MOH Permanent Secretary convened a SHIMS Steering Committee to ensure that the study's implementation is scientifically sound, ethical, and of high quality. The composition of the Committee makes it well-suited to continuously review the M&E data from programs and preliminary/intermediate study data (including HIV incidence estimates from Cohort A1). The Principal Investigators are represented on the Committee. The Committee meets bi-weekly, or more or less frequently if needed, and will include as a standing order of business the review of updated M&E data. Steering Committee teleconferences will occur quarterly with the participation of the all Principal Investigators and a majority of Co-investigators, specifically to review the ASI and ART program M&E data as relate to the SHIMS. Any necessary adjustments to the survey/cohort sample sizes, cohort follow-up durations, time period between surveys/cohorts, or other additions/modifications to the study will be at the discretion of the Principal Investigators.

8.1.2 Descriptive analyses

Descriptive analyses will include: a description of all individuals who are offered participation but refused in either the pre-cohort survey or longitudinal cohorts; characteristics of all individuals who consent to participate; and a description of all individuals who are enrolled in the longitudinal cohorts, including those lost to follow-up.

8.1.3 Analysis of primary objectives: Comparison of HIV incidence rates

Primary Objectives 1a & 1b and 2a & 2b

Comparisons of rates of seroincidence in the pre vs post MC ASI will compare incidence rate ratios assuming a Poisson distribution of seroconversions in the follow-up time in each cohort. The HIV seroincidence rates, computed as the total number of seroconversions divided by the total number of person years, adjusted by sampling weights to achieve a population, age, and gender based estimate of seroincidence will be compared in the pre vs post MC ASI in Cohorts A1 and A2. The statistic is the Wald test statistic for the slope of a Poisson regression with a binary covariate for pre vs post MC ASI. Cohorts A1 and A2 are based on independent samples. Each is intended to be representative of the contemporary Swaziland population, thus the sample weighting in each cohort will be based on current population estimates. s

For men in the baseline cohort (Cohort A1) who become circumcised between the time of cohort enrollment and follow-up, only person years prior to circumcision will be included in the analysis. All follow-up time from men who are circumcised prior to enrollment, and men who remain uncircumcised at follow-up, will be included. All follow-up time from women will be included.

To account for potential dependence of HIV seroincidence within households a sensitivity analysis using bootstrap resampling techniques will assess the effect of sampling multiple people from each household on the primary analysis.

Sensitivity analyses will be conducted to assess the impact of any population based demographic changes in the HIV-uninfected population between the pre and post MC ASI periods.

Primary Objective 3

Comparisons of rates of seroincidence in the circumcised vs. uncircumcised men in the post-MC ASI male cohorts will compare incidence rate ratios assuming a Poisson distribution of seroconversions in the follow-up time in each group. The HIV seroincidence rates, computed as the total number of seroconversions divided by the total number of person years in each group, adjusted by the cohort sampling weights to achieve a population age-based estimate of seroincidence will be compared in the circumcised vs. uncircumcised men. The statistic is the Wald test statistic for the slope of a Poisson regression with a binary covariate for circumcision.

Person years of men who are uncircumcised at the time of cohort enrollment and become circumcised during the 12-month follow-up period will be included in the uncircumcised follow-up until time of circumcision, and in the circumcised follow-up after the time of circumcision.

The exploration of factors that are significant effect modifiers and/or confounders of HIV seroincidence between these two groups will be used to further understand observed differences.

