5.2.1 HIV status

During each contact with participants, consenting adults will be tested for HIV for this study using a serial algorithm for rapid tests approved by the Swaziland National Reference Laboratory. This algorithm includes the use of the 4th generation Determine rapid test kits that are capable of detecting HIV antigens. Samples from persons that are

HIV antigen reactive will subsequently be tested using both enzyme immunoassay (EIA) and nucleic acid detection tests (NAT) in the laboratory (Appendix A). NAT are HIV-discriminatory assays approved by the FDA to detect HIV-1 protein/antigens, which are produced by the body prior to the production of antibodies. NAT will be used in this protocol to identify people who were very recently HIV-infected who might not have had their HIV infection detected if only rapid HIV tests that detect antibodies were being used. The use of HIV antigen detection tests is to avoid enrollment of acutely HIV-infected individuals into the cohorts.

1. Confirmed HIV-negative: Negative per the serial algorithm for rapid HIV testing that includes 4th generation Determine, approved for this study. See Appendix A.
2. Confirmed HIV-positive: Positive per the serial algorithm for rapid HIV testing that includes 4th generation Determine, approved for this study. See Appendix A.

Sub-categories defining duration of HIV infection among confirmed HIV-positive persons are as follows:

- HIV-positive Incident Infection: identified by direct observation of HIV seroconversion during the period of participation in the cohort, i.e. a person was confirmed HIV-negative at cohort enrollment and confirmed HIV-positive at cohort follow-up.
 - HIV-positive Non-recent/Prevalent Infection: identified as HIV-positive as part of the pre-cohort survey based upon the serial algorithm for rapid testing approved for this study. See Appendix A.
3. HIV indeterminate: Indeterminate per the serial algorithm for rapid HIV testing that includes 4th generation Determine, approved for this study. See Appendix A.

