6.2.4 Follow-up Visits

Cohort A1 and A2 participants will be visited again at their place of residence for a follow-up visit at 6 months (Cohort A1) or 12 months (Cohort A2) after enrollment.

For each follow-up appointment at the home, at least 3 attempts will be made by study staff to establish contact in person and complete the follow-up visit activities. Visits will

ideally be completed within a specified ± 14 day window around target follow-up dates. The allowable follow-up dates, however, will extend to the date of study conclusion. Detailed information regarding visit windows will be thoroughly described in the SHIMS SOP on retention. The following procedures/assessments are to be performed at the cohort follow-up study visits:

- Verification of the participant's identity and participation in the study
- Selection of a relatively private location either inside or outside the participant's home, so that the follow-up visit may take place with as much privacy as possible, as appropriate review of the study goals and procedures
- For men, an interviewer-administered questionnaire to detect changes in self-reported MC status
- Participants who were uncircumcised at cohort enrollment but circumcised at cohort follow-up will be asked to provide information about the date and location of the MC surgery (Appendix K). Their medical records related to their MC surgery will be abstracted at the facility that performed the MC surgery to determine the date of surgery.
- Blood draw of approximately 7-10mL
 - HIV testing and counseling using the serial algorithm for rapid HIV testing that is approved for this study (Appendix A).
 - See procedures outlined in Section 6.1.2.1-6.1.2.3 for instructions on handling HIV test results.

Those who decline cohort follow-up will be thanked for their time and asked to provide basic information about their reason for refusal to assist in characterizing the impact of refusal on study outcomes. This information will be documented in the appropriate section of the Short/Long-term Cohort Follow-up CRF(s) (Appendices K-N).

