6.2.4.1 Additional Study procedures for participants who test HIV-positive at the follow-up visit

- Interviewer administered questions to assess whether the participant has previously tested HIV-positive and whether HIV care and treatment has been sought.
- Counseling about the benefits of HIV care and treatment services and provision of information to help them link to these services.
- Counseling regarding importance of HIV testing of partners and referral to HIV testing sites.
- Male participants identified as newly circumcised **and** newly HIV-infected at follow-up (were uncircumcised at cohort enrollment) will be asked to provide information about the date and location of the MC surgery, whether they had an HIV test the day of the MC surgery, and the HIV test result, to help determine HIV status at the time of circumcision. Their medical records related to their MC surgery will be abstracted at the facility that performed the MC surgery to determine whether an HIV test was conducted pre-operatively and the results of the test, if done.

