8.9 Limitations of study

We propose a novel approach with population-based repeated short-term longitudinal cohort studies in addition to a longer-term longitudinal cohort to evaluate changes in HIV incidence before and after the MC ASI campaign. It is possible that other ongoing

factors occurring simultaneously may contribute to any observed changes (or lack of) in HIV incidence. To help infer the role of MC in the observed changes in HIV incidence, we will capture data from participants experiencing other interventions and account for these in analyses.

We anticipate an 8-12% annual lost-to-follow-up rate among cohort participants at follow-up due largely to movement within Swaziland or migration. There is a possibility that those who migrate and those who do not are different from each other in meaningful ways related to HIV infection risk. We have mitigated the effect of the migration on the evaluation by incorporating lost-to-follow-up into study calculations to ensure sufficient power is maintained.

Data on sexual behaviors (such as past/current number of partners, condom use, etc.) and history of STI symptoms will be self-reported and are thus subject to potential recall bias and social desirability bias. However, efforts will be made to ensure that the study staff recruiting, enrolling, interviewing and performing the blood sample collection will not be from within the community under evaluation. This should minimize concerns about stigma and disclosing personal information during data collection. There is also a possibility that self-reported circumcision status may be incorrect, despite the use of illustrations.

Persons who are in institutions such as prisons are not included in the study; persons who are transient and thus not at home during enrollment are also not captured.

Though every attempt will be made to determine HIV status at the time of circumcision for male participants in the post-intervention longitudinal cohorts identified as having become both circumcised and HIV infected since the prior assessment, it is possible that some men retrospectively determined to have been HIV-negative at the time of circumcision will in fact have been HIV-positive, and vice versa. A special questionnaire, review of surgical records, and laboratory assays will be performed.

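### Section 8.1.3 cuts the person-time of newly circumcised A1 men at surgery but gives no matching cut for their seroconversions, so a literal reading overstates the pre-campaign rate and the reduction

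*Protocol*

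**What the plan says.** Section 8.1.3 (Primary Objectives 1a, 1b, 2a and 2b) defines the incidence rate as "computed as the total number of seroconversions divided by the total number of person years, adjusted by sampling weights". For A1 men circumcised between enrolment and follow-up, "only person years prior to circumcision will be included in the analysis". Under Objectives 1 and 2 there is no such cut for the post-campaign cohort (A2).

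Section 5.2.1 defines an incident infection: "a person was confirmed HIV-negative at cohort enrollment and confirmed HIV-positive at cohort follow-up". Section 5.2 applies its definitions throughout the study, and none refers to a surgery date. Section 6.2.4 schedules one study retest, at a "follow-up visit at 6 months (Cohort A1) or 12 months (Cohort A2) after enrollment".

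Section 6.2.4.1 covers both A1 and A2. For men found newly circumcised and newly infected, it abstracts the surgical record "to determine whether an HIV test was conducted pre-operatively and the results of the test, if done". Section 8.1.3 does not refer to these data. Section 8.9 describes determining HIV status at circumcision only "for male participants in the post-intervention longitudinal cohorts identified as having become both circumcised and HIV infected since the prior assessment".

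For Objective 3, the person years of men circumcised during A2 follow-up are "included in the uncircumcised follow-up until time of circumcision, and in the circumcised follow-up after the time of circumcision". Nothing says to which side the seroconversion goes.

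**The concern.** A rate is interpretable only if its numerator and denominator cover the same time at risk. Take an A1 man circumcised at month 2 and found positive at month 6. Under the literal rules he contributes one event on two months of person-time, even if he was infected after surgery. Such events raise the A1 rate.

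The cut applies to A1 only, so the A2/A1 rate ratio is pushed toward a reduction. That ratio, in men, is Objective 1a, the comparison that section 7.1 says the study is powered for. In Objective 3 the lack of an allocation rule could credit a switcher's infection to the wrong circumcision group.

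**Working it through.** **1. The plan's own figure.** Inputs from section 7.2: 2.0 against 1.1 per 100 person years, person years 1:2, two-sided alpha 0.05, 80% power, Wald test in Poisson regression.

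T = (z₀.₉₇₅ + z₀.₈₀)² × [1/(λ₁/3) + 1/(2λ₂/3)] / ln(λ₂/λ₁)², with λ₁ = 0.020 and λ₂ = 0.011, gives 6,288.7 person years (stated 6,288 in the text and 6,289 in Table 1), split 2,096 and 4,192. With the design effect of 1.25 and retention of 90% and 85%:
- A1: 2,096 × 1.25 / 0.90 / 0.5 = 5,822 men (stated 5,823)
- A2: 4,192 × 1.25 / 0.85 = 6,165 men (stated 6,165)

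The design reproduces and is not affected by this point.

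**2. Size of the mismatch.** Assumptions:
- A share c of A1 men is circumcised during follow-up. The protocol gives no value.
- Surgery dates are uniform over follow-up, so half of each such man's time is cut.
- The incidence rate after surgery is h times the rate before. The range runs from h = 0.46, the meta-analytic ratio cited in section 7.2, to h = 1.
- Every seroconversion is counted.

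Inflation of the A1 rate = (1 − c/2 + h·c/2) / (1 − c/2). The reduction that would appear if the true A1 and A2 rates were equal is 1 − 1/inflation.

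Example, c = 5%: (0.975 + 0.46 × 0.025)/0.975 = 1.012 at h = 0.46, and 1/0.975 = 1.026 at h = 1.

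| c | Inflation, h = 0.46 to 1 | A1 rate if true rate is 2.0 | Spurious reduction |
|---|---|---|---|
| 2% | 0.5% to 1.0% | 2.01 to 2.02 | 0.5% to 1.0% |
| 5% | 1.2% to 2.6% | 2.02 to 2.05 | 1.2% to 2.5% |
| 20% | 5.1% to 11.1% | 2.10 to 2.22 | 4.9% to 10.0% |
| 36% | 10.1% to 22.0% | 2.20 to 2.44 | 9.2% to 18.0% |

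The 36% row is a ceiling from section 2.1. HIV-negative men number 0.80 × 240,000 = 192,000, and the target is 140,000 circumcised in 12 months, so 140/192 × 6/12 = 0.36. It requires every A1 man's full six months to fall inside an on-target campaign.

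**3. Effect on the test.** With equal true rates of 2.0, A1 effective time 2,096 × (1 − c/2) and A2 effective time 4,192, the chance of a falsely significant reduction (nominally 2.5%) is 2.9% to 3.4% at c = 5% and 4.4% to 8.0% at c = 20%.

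**4. The opposite handling is also biased.** At c = 10%, dropping every infected switcher while keeping his pre-surgery time gives 2.0 × 0.90/0.95 = 1.90 per 100 person years. Keeping every event gives 2.05 to 2.11. An event rule is needed either way.

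**5. Can A1 overlap the campaign?** Section 4 schedules A1 from month −6 to month 0, with month 0 the January 2011 launch. Section 7.2 has household listing running from November 2010 to May 2011, and listing precedes household sampling. Section 6.2.4 lets follow-up visits extend to study conclusion. Some overlap is therefore likely; its extent is not stated.

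**The case against.** The strongest reply is that 8.1.3 never says post-surgery events are kept. It assumes a Poisson count of seroconversions in the follow-up time, so if only pre-surgery time enters the analysis, the natural reading is that only pre-surgery events do. Section 6.2.4.1 supports that intent, and event dating is detail a statistical analysis plan may carry. This stands in part: retention of the events follows from the formula and the case definition, not from any sentence about switchers. But the protocol itself fixes the rate formula, the case definition and the person-time rule, and they do not fit together. Section 8.1.3 uses none of the pre-operative data, and 8.9 leaves A1 out.

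A reader might infer that the only HIV test comes after surgery. That is true only of study tests. The campaign includes pre-operative testing (section 2.1), and any result is abstracted for A1 men too.

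A reader might also take the 10% to 22% figure as expected. It is not. It needs full overlap, and its upper end needs no protection from circumcision. At 5% circumcised, the inflation is under a fifth of the A1 rate's relative standard error, which is about 15% (2,096 × 0.02 = 42 effective events; 1/√42 = 0.154).

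Finally, Objective 3 is better covered than Objective 1a. For post-campaign men, 8.9 promises a questionnaire, surgical record review and laboratory assays, and admits residual misclassification. What is missing there is only the allocation rule in the analysis.

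**Conclusion.** The point holds in conditional form. Followed literally, the rules in 8.1.3 and 5.2.1 truncate the time of A1 men circumcised during follow-up but not their events. This biases the A1 male rate, and the apparent reduction on Objective 1a, upward. The documents do not establish that post-surgery events will in fact be kept, nor that the bias is large.

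The inflation is about 1% or less if A1 ends at launch and only 1% to 2% of men switch, 1.2% to 2.6% at 5% circumcised, 5% to 11% at 20%, and 10% to 22% as a ceiling. All these figures rest on an assumed share circumcised, uniform surgery dates and a post-surgery rate ratio between 0.46 and 1. Because the correction needs only data already planned, it should be made.

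**What to change.** **Objective 1a, section 8.1.3.** State that events and person-time of A1 men are truncated together, so that a seroconversion counts only if infection is placed before surgery.
- Pre-operative result positive: count the event.
- Pre-operative result negative: exclude the event along with the post-surgery time, noting the misclassification that 8.9 admits.
- No result: multiply impute the infection date, and bound the answer by counting all such events and then none.

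**Sensitivity analysis.** Report the A1 rate with all person-time and all events, which matches how A2 is handled in Objective 1a.

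**Objective 3.** Allocate switchers' events with the same pre-operative data. For men without a result, use a method that allows different hazards before and after circumcision. A proportional time split assumes equal hazards and would pull the circumcision effect toward the null.

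**Section 8.9.** Extend the wording on HIV status at circumcision to A1.

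**Cost.** Analysis wording only. The surgery date, and the pre-operative result where a test was done, are already collected. If 5% to 20% of A1 men switch, matched truncation lowers power from 80.0% to between 79.5% and 77.7%; that loss comes from the person-time cut the protocol already makes. The small downside is that a few events carry imputed timing.
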